### **14. Potential Benefits to Participants**

Hematopoietic stem cell transplant (HSCT) is associated with an array of negative symptoms that affect long-term QOL, and these symptoms occur during a requisite period of

hospitalization and physical isolation, as the average hospitalization for transplantation is 2-3 weeks. Intervening on the emotional and social symptoms during HSCT may reduce depression and improve QOL, which is so critical for well-being and survival.

Previous research from our group found that a single session of chaplain-delivered CSH reduced depression and anxiety among hospitalized inpatients (paper in progress). Patients in this study may directly benefit from CSH. Moreover, this feasibility study will establish the manualized protocol and intervention delivery process that can be further evaluated in future research.

### **15. Compensation to Participants**

There is no financial compensation for participation.

### **16. Data Analysis, Management and Confidentiality**

#### **Statistical analysis**

**Measuring and evaluating retention:** Based on a large randomized trial of exercise and stress management programs for patients receiving blood and marrow transplant, we expect that:

- Benchmark 1: 29 (97%) patients enrolled in the study will complete at least one session of chaplain-delivered CSH, based on the fact that 3% of patients enrolled in the larger trial did not receive an intervention).
- Benchmark 2: We will lose 7 patients throughout the trial and thus have complete data from 23 patients (78.8%), based on the Day 100 completion percentage from the trial cited above (78.8%).

We believe this is a conservative estimate because the 78.8% Day 100 completion rate reported in the previous study is approximately 2.5 month past our final time point for this aim.

**Measuring and evaluating adherence:** While chaplains will intend to deliver 8 sessions of CSH during HSCT, we may find that patients are too sick to receive all 8 sessions or that they drop out of the study prior to the completion of all 8. We may also find that chaplains do not deliver the intervention with fidelity during all 8 sessions. Adherence will be evaluated as the percent of sessions completed by patients and characterized as “low” (< 70%), “moderate” (70-80%) and “high” (> 80%) adherence.

- Benchmark 1: We expect that all chaplain residents will achieve high levels of adherence.
- Benchmark 2: We expect that 23 patients will begin the intervention, complete at least one session of CSH and remain in the study until the end of HSCT (see retention benchmarks below), completing at least 75% (6 out of 8) CSH sessions.

**Protocol Title: A feasibility study of Chaplain-delivered compassion meditation for patients receiving stem cell transplantation.**

---

**Data collection:** We will collect audio recordings from all CCSH sessions conducted with enrolled participants. All sessions will be transcribed verbatim, and two CCSH experts will independently evaluate fidelity of implementation (FOI) in a random subset of 50% of the sessions. From the transcripts, coders will quantify 4 dimensions of fidelity according to a recent guide for FOI in meditation studies:

1) Accuracy (sometimes referred to as *adherence* but called *accuracy* here to avoid confusion with overall adherence): the extent to which the core elements of CCSH were implemented as intended. Accuracy will be evaluated as the percent of session components implemented by chaplains and characterized as “low” (< 70%), “moderate” (70-80%) and “high” (> 80%) accuracy.

2) Dosage: quantified as the amount (percentage) of CBCT that patients receive. We will also characterize the modal number of sessions received as well as the range of sessions completed by all patients. From the range, we will create categories of “low”, “medium”, and “high” dosage that we will use as categorical groups in future studies.

3) Quality: extent to which the chaplain delivered the content as intended. We will generate average competency ratings for each chaplain as well as overall average quality ratings.

4) Responsiveness: the extent to which patients were engaged in each session, operationalized as “maximally,” “moderately”, or “minimally” enthusiastic and attentive during each. We will quantify the average patient engagement for all sessions, as well as the average responsiveness for each session (i.e., 1st – 8th).

In addition, I will quantify Accuracy, Dosage, and Responsiveness from chaplain checklists that chaplains complete after each session.

- Benchmark 1: We will be able to quantify FOI for all chaplain sessions and generate an average FOI for each chaplain
- Benchmark 2: We expect all chaplains will deliver CCSH with high levels of fidelity.

Audio files will be stored for one year after transcription is complete. All other data will be stored for at least 5 years as de-identified data and secured on a password protected Emory server. Only the IRB-approved study team will have access to the data. The PI ([name]) will be responsible for storage and maintenance and destruction of the data.

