## Table of Contents

1. Study Summary .....	4
2. Objectives.....	Error! Bookmark not defined.
3. Background .....	Error! Bookmark not defined.
4. Study Endpoints .....	7
5. Study Intervention/Design .....	7
6. Procedures Involved.....	7
7. Study Timelines .....	8
8. Inclusion and Exclusion Criteria .....	Error! Bookmark not defined.
9. Population .....	Error! Bookmark not defined.
10. Local Number of Participants.....	Error! Bookmark not defined.
11. Recruitment Methods .....	Error! Bookmark not defined.
12. Withdrawal of Participants .....	Error! Bookmark not defined.
13. Risk to Participants.....	9
14. Potential Benefits to Participants .....	Error! Bookmark not defined.
15. Compensation to Participants .....	Error! Bookmark not defined.
16. Data Analysis, Management and Confidentiality .....	Error! Bookmark not defined.
17. Provisions to Monitor the Data to Ensure the Safety of Participants .....	Error! Bookmark not defined.
defined.	
18. Provisions to Protectd the Privacy Interest of Participants .....	11
19. Economic Burden to Participant .....	Error! Bookmark not defined.
20. Informed Consent .....	12
21. HIPPA.....	Error! Bookmark not defined.
22. Setting .....	Error! Bookmark not defined.
23. Resources Available.....	13
24. References.....	14

1. Study Summary

Study Title	A feasibility study of Chaplain-delivered compassion meditation for patients receiving stem cell transplantation.
Study Design	The study will be an open-pilot trial of chaplain-delivered CCSH to examine chaplain fidelity to CCSH.
Primary Objective	To examine the adoption, extent of implementation, and fidelity of chaplain-delivered CCSH.
Secondary Objective(s)	The second goal is to make refinements as necessary.
Research Intervention(s)/Interactions	Compassion Centered Spiritual Health (CCSH)
Study Population	The study participants for this aim will be (1) Chaplains who have already completed the formal educational course as part of their residency training and willingly volunteer to participate. There will be no exclusion criteria and no consequence to the chaplains for refusing to volunteer. (2) The patients they see during consultation are also part of the study population.
Sample Size	6-8 chaplains 50 stem cell patients
Study Duration for individual participants	8 months

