#### **6. Procedures Involved**

Chaplains will be asked to volunteer to participate and be consented according to standard IRB-approved protocols. We will enroll a convenience sample of 6-8 chaplains who have already completed the formal CCSH educational course.

[name] (PI) will work with collaborators and CCSH experts to identify the core components of chaplain-delivered CCSH and to develop an objective fidelity-coding manual that we will use to evaluate the fidelity of chaplain-delivered CCSH for patients during HSCT. We will utilize FOI theoretical frameworks to identify structural components (the content that is delivered) and process components (the manner in which chaplains implement content).

1. Chaplains will deliver between four and eight 30-minute sessions (2-4/week) of CCSH to up to 50 adult patients with multiple myeloma or lymphoma during their admission for HSCT. CCSH sessions will be delivered in the patient’s room. The number of sessions between four and eight will be determined based on patient availability, interest, and feasibility. Based on the interviews with staff, we will work within the cancer unit’s workflow to minimize any interference with medical care. Before the chaplain completes each session, we will administer the (<1 min) NCNN Distress Thermometer, a single-item distress thermometer that compares favorably with longer measures used to screen for distress.

2. Chaplains will complete a post-visit fidelity checklist after each session to report which of the key intervention activities were completed.

**Protocol Title: A feasibility study of Chaplain-delivered compassion meditation for patients receiving stem cell transplantation.**

---

3. To rigorously assess fidelity, the study team will collect audio recordings of all CCSH sessions. All sessions will be transcribed verbatim, and two CCSH experts will independently evaluate the extent to which chaplain residents deliver CCSH with fidelity in a random subset of 50% of the sessions. The audio transcripts will be secured on a password-protected Emory server for one year after transcription and will then be destroyed.

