## **7. Study Timelines**

Individual subject participation: approximately 8 months

Chaplain study participants will deliver between four and eight 30-minute sessions (2-4/week) of CSH to 30-50 adult patients with multiple myeloma or lymphoma during their admission for autologous HSCT. We expect recruitment will take up to 8 months.

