## **10. Local Number of Participants**

This is not a multi-site study.

We will enroll a convenience sample of 6-8 chaplains. The 2018 entering class of chaplain residents is 47% male, and 88% non-white. We expect to enroll 50% women, and 50% non-white chaplains.

Chaplains will deliver eight 30-minute sessions (4/week) of CCSH up to 50 adult patients with multiple myeloma or lymphoma during their admission for autologous HSCT. Based on a previous pilot study of yoga with hospitalized HSCT patients, we anticipate that 37% of the patients will be men, and 44% will be non-white.

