## **23. Resources Available**

It is expected that enrollment will take place from November 2021 through July 2022.

To recruit patients for this study, we will engage with referring physicians in Emory's Bone Marrow and Stem Cell Transplant Center. We will arrange to give a presentation at the Emory Huddle and/or the center's grand rounds so that providers and staff are familiar with the study.

Lost to follow-up: The funder (NCCIH) considers lost to follow-up as a research subject who was participating in the study at a certain point in time and subsequently missed two consecutive study visits and is unresponsive to study contact or is no longer participating in study activities.

We base our calculations on a large randomized trial of exercise and stress management programs for patients receiving blood and marrow transplant, in which the 120-day lost-to-follow-up was 30.8%. Of 711 consented and randomized, the researchers received final surveys from 492 patients (69.2%): 5 (0.7%) did not undergo HCT, 21 (3.0%) did not receive the intervention, 37 (5.2%) died before Day 100, and 48 (6.8%) died between Day 100 and day 180.

Based on these data, we expect that 97% patients enrolled in the study will complete at least one session of CSH (based on the fact that 3% of patients enrolled in the larger trial withdrew prior to receiving an intervention). Based on the Day 100 completion percentage from that trial (78.8%), we expect that we will have complete data from 78.8% of enrolled patients. However, this is a conservative estimate, given that the 78.8% Day 100 completion rate reported in the previous study is approximately 2.5 month past our final time point for this aim.

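### The patient counts in the Section 16 benchmarks (29, 7, 23 and the reused 23) fit an enrolment of 30, not the 50, up to 50, or 30-50 stated elsewhere

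*Protocol*

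**What the plan says.** Section 16 of the protocol, under the retention heading, gives two patient-level benchmarks. The first is "Benchmark 1: 29 (97%) patients enrolled in the study will complete at least one session of chaplain-delivered CSH". The second is "We will lose 7 patients throughout the trial and thus have complete data from 23 patients (78.8" (the last figure is a percentage). Under the adherence heading the same number returns: "We expect that 23 patients will begin the intervention, complete at least one session of CSH and remain in the study", with at least 6 of 8 sessions completed. That benchmark gives no percentage of enrolled patients and refers the reader to the retention benchmarks. Section 16 names no enrolment figure for any of these counts.

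Planned patient enrolment appears in four other places:

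- Section 1, sample size row: "6-8 chaplains 50 stem cell patients".
- Section 6: "to up to 50 adult patients with multiple myeloma or lymphoma during their admission for HSCT".
- Section 7: "30-50 adult patients with multiple myeloma or lymphoma during their admission for autologous HSCT".
- Section 10: "up to 50 adult patients with multiple myeloma or lymphoma during their admission for autologous HSCT".

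Section 23 repeats the two retention expectations as percentages only. For the second it says "we expect that we will have complete data from 78.8% of enrolled patients".

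**The concern.** The Section 16 counts look as if they were worked out for a trial of 30 and not updated when enrolment was set at up to 50. If so, each retention benchmark holds a count and a percentage that part company as enrolment rises, and the second adherence benchmark is a fixed count that becomes easier to reach with every patient added.

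This is a feasibility study with no hypothesis test. The benchmarks are its stated numerical yardsticks for patient retention and for how many patients reach the session target, and the number of sessions completed is the secondary outcome in Section 4. Section 17 also has retention and attrition reported to the monitoring committee twice a year. Suppose 50 patients enrol and 30 have complete data (60%). The trial then exceeds 23 but falls short of 78.8%, and the protocol does not say which of the two figures governs.

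**Working it through.** **Inputs.** From Section 16: 29 patients (97%) with at least one session; 7 lost; 23 (78.8%) with complete data; 23 again in the second adherence benchmark. From Sections 1, 6, 7 and 10: 50, up to 50, 30-50 and up to 50. From Section 23: 97% and 78.8% of enrolled patients.

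**Step 1: recover the enrolment behind the counts.**

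- Lost plus complete: 7 + 23 = 30.
- First retention benchmark: 29 / 0.97 = 29.9. Checking whole numbers, 29/29 = 100%, 29/30 = 96.7% and 29/31 = 93.5%, so only 30 rounds to 97%.
- Second retention benchmark: 23 / 0.788 = 29.2, which is close to 30 but not exact (see step 2).

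**Step 2: reproduce the plan's figures at 30.**

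- At least one session: 0.97 × 30 = 29.1, so 29.
- Complete data: 0.788 × 30 = 23.64. This gives 23 if rounded down and 24 if rounded to nearest.
- Lost: 30 − 23 = 7.

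The printed counts reproduce at 30, with the complete-data figure rounded down. Even there 23/30 is 76.7% and not 78.8%, but that is only a rounding slip.

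**Step 3: apply the same rates and counts across the stated enrolment range.** For enrolment N, the expected numbers are 0.97N starting, 0.788N with complete data and 0.212N lost. The fixed counts as shares of N are 29/N and 23/N; losing 7 leaves (N − 7)/N.

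| N | Expected to start | Expected complete | Expected lost | 29 as share of N | 23 as share of N | Retained if 7 are lost |
|---|---|---|---|---|---|---|
| 30 | 29.1 | 23.6 | 6.4 | 96.7% | 76.7% | 76.7% |
| 40 | 38.8 | 31.5 | 8.5 | 72.5% | 57.5% | 82.5% |
| 50 | 48.5 | 39.4 | 10.6 | 58.0% | 46.0% | 86.0% |

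At 50, the one sentence that forms the second retention benchmark yields three different completion rates: 86% from the number lost, 46% from the number complete, and 78.8% as printed. At 40 the three are 82.5%, 57.5% and 78.8%.

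**Step 4: check what rescaled counts would mean.** If true retention is exactly 78.8% and 50 enrol, the number with complete data follows a Binomial(50, 0.788) distribution, treating patients as independent. Then P(39 or more) = 0.633 and P(40 or more) = 0.500. A rescaled count describes what to expect. Used as a pass mark, it would fail a trial that performs exactly as expected between about a third and half of the time.

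**The case against.** Five points can be made for the plan.

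- **Thirty lies within the planned range.** It is the floor in Section 7, and a ceiling of 50 permits it; only Section 1 gives a flat 50. This is true, and it limits the outright contradiction to Section 1. But the counts are not labelled as a lower-bound scenario, and they fail over the rest of the range.
- **The rates are primary.** Section 16 derives its retention counts from percentages in an earlier trial, and Section 23 restates them without counts. This stands for the two retention benchmarks: a careful reader can recover the intended rates.
- **The adherence benchmark can be rescued the same way.** It refers to the retention benchmarks, where 23 is labelled 78.8%. This helps only in part. The reference leads to a count and a percentage that disagree above 30, and the 75% printed in the adherence benchmark is a share of sessions, not of patients.
- **These are forecasts, not thresholds.** The wording is one of expectation, no progression rule uses the counts, and the primary endpoint is fidelity. This stands and limits the consequence. A forecast called a benchmark will still be compared with the results.
- **The pair 23 and 78.8% does not match exactly at 30 either.** Correct, as step 2 shows. That adds a small slip and does not remove the larger one.

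**Conclusion.** The concern holds. The Section 16 counts belong to an enrolment of 30 and are wrong for any enrolment well above it. At the planned maximum of 50, the printed 97% and 78.8% correspond to about 48-49 patients starting, 39-40 with complete data and about 11 lost, against the stated 29, 23 and 7. The most exposed item is the second adherence benchmark, which as written would be met by 46% of 50 patients although it appears to have been set at about 77% of 30.

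This conclusion takes the printed percentages as the intended rates, with enrolled patients as the denominator, as Section 23 does. The session-adherence bands (below 70%, 70-80%, above 80%) do not depend on enrolment and are unaffected. With no progression rule and no power calculation resting on these counts, the fault is one of reporting and interpretation. It should be fixed, but it does not threaten the trial's conduct.

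**What to change.** 1. Reconcile the enrolment statements in Sections 1, 6, 7 and 10. A range or a ceiling is acceptable if it is the same throughout.
2. State the three patient-level benchmarks in Section 16 as percentages of enrolled patients. For retention these are the 97% and 78.8% already in Section 23.
3. Give the second adherence benchmark its own percentage of enrolled patients in place of the bare 23.
4. If counts are kept, show them only as illustrations for a stated enrolment: about 29 starting and 24 with complete data at 30, or 48-49 and 39-40 at 50. Say that they are expected values and not pass marks.

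The cost is protocol wording only: no extra patients, visits or data. The change is best made before results are compared with the benchmarks.

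### The protocol never says that 8 sessions is the target and 4 the minimum, and adherence Benchmark 1 holds chaplains to a measure defined by what patients complete

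*Protocol*

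**What the plan says.** **Dose.** The protocol describes the number of sessions in four places.

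- Section 6 gives a range of four to eight at 2-4 per week and adds: "The number of sessions between four and eight will be determined based on patient availability, interest, and feasibility".
- Section 7 repeats the range: chaplains will "deliver between four and eight 30-minute sessions (2-4/week) of CSH".
- Section 10 gives a single number and a single frequency: "Chaplains will deliver eight 30-minute sessions (4/week) of CCSH".
- Section 16, in the paragraph on adherence, opens with "While chaplains will intend to deliver 8 sessions of CSH during HSCT" and allows that patients may be too sick to receive all 8 or may drop out.

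**Measure.** Section 16 then defines it: "Adherence will be evaluated as the percent of sessions completed by patients and characterized as" low (below 70%), moderate (70-80%) or high (above 80%).

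**Benchmarks.** Adherence Benchmark 1 is about chaplains: "We expect that all chaplain residents will achieve high levels of adherence". Adherence Benchmark 2 is about patients. It expects 23 who start, remain to the end of HSCT and meet the criterion "completing at least 75% (6 out of 8) CSH sessions".

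**The chaplains' own delivery.** Later in Section 16 this is measured under another name. Accuracy is the percentage of session components that chaplains implement, with the same 70% and 80% cut-offs. The text says that the name was chosen so that it is not confused with overall adherence. A separate benchmark in the fidelity (FOI) list expects all chaplains to reach high fidelity.

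**The concern.** There are two separate problems.

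The first is the dose. A chaplain who follows Section 6 may plan and deliver a 4-session course and comply fully. Under Section 10 the same course is half of what is stated, and under Section 16 it is half of what is intended. Without a sentence that makes 8 the target and 4 the minimum, a low percentage can mean a permitted short course or a patient who stopped early. In a feasibility study these point to different remedies: one concerns scheduling and the dose, the other tolerability and dropout.

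The second is the unit. Benchmark 1 judges chaplains, but the only adherence measure in the protocol counts sessions that patients complete. Taken literally, a chaplain could fall short because patients became too ill or withdrew, which are the very reasons Section 16 gives for incomplete courses.

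**Working it through.** **Inputs.** Permitted sessions: 4 to 8 (Sections 6 and 7). Intended sessions: 8 (Section 16). Bands: low below 70%, moderate 70-80%, high above 80% (Section 16). The sentence that defines adherence does not name its denominator. The number 8 comes from the sentences before it and from Benchmark 2, and Section 16 offers no other.

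**The plan's own figure.** 6 / 8 = 75%, which reproduces the threshold in Benchmark 2.

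**Permitted courses, each fully attended, scored against 8 and banded per patient (an assumption; the level is not stated).**

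| Sessions | Sessions / 8 | Band | At least 6 of 8 |
|---|---|---|---|
| 4 | 50% | low | no |
| 5 | 62.5% | low | no |
| 6 | 75% | moderate | yes |
| 7 | 87.5% | high | yes |
| 8 | 100% | high | yes |

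Two of the five permitted lengths are low, and high needs at least 7 sessions. This counts lengths and not patients; the protocol does not say how many patients will have short courses.

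**Frequency.** Sections 3 and 14 put the average transplant stay at 2-3 weeks. If sessions ran through such a stay at the permitted 2 per week, a fully attended course would be 2 x 2 = 4 to 2 x 3 = 6 sessions, or 50% to 75%, and would never be high. At 4 per week, 2 weeks give 4 x 2 = 8. So the difference in frequency between Sections 6 and 7 and Section 10 leads directly to a difference in band.

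**Benchmark 1.** The protocol gives no rule for turning patient completion into a chaplain score. As an illustration only, assume that sessions are pooled over each chaplain's patients. Section 7 plans for "30-50 adult patients with multiple myeloma or lymphoma", and there are 6-8 chaplains, so the caseload is between 30 / 8 = 3.75 and 50 / 6 = 8.3 patients. Take a chaplain with 4 patients (4 x 8 = 32 intended sessions), three of whom complete all 8:

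- the fourth withdraws after 1 session: (8 + 8 + 8 + 1) / 32 = 25 / 32 = 78.1%, moderate;
- the fourth withdraws after 2 sessions: (8 + 8 + 8 + 2) / 32 = 26 / 32 = 81.3%, high.

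In both cases the shortfall comes entirely from the patient's withdrawal. The example shows how the benchmark would work, not how often it would be missed.

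**The case against.** **8 is plainly the intended dose.** Section 16 says so, and Section 6 gives the lower limit, so target and minimum are both in print. A feasibility study should learn whether patients can take the intended dose, and 4 of 8 scored as low against that dose is informative. This stands. A reader might infer that the low label is itself an error or that the bands are wrong; the protocol does not support that. What remains is that no sentence joins the two numbers, that Section 10 gives eight with no lower limit, and that the label alone does not show why a course was short.

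**The level of banding is not stated.** The bands could apply per patient, per chaplain or to the pooled total, and an analysis plan might settle this. This also stands, so the 50% and 62.5% results are conditional on per-patient use.

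**Benchmark 2 is a cohort count.** It might be inferred that a short course fails Benchmark 2. It does not: the benchmark asks for 23 patients, and a patient with 4 or 5 sessions is simply not among them.

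**Benchmark 1 may be a slip of terms.** The sentence just before the definition mentions chaplains not delivering with fidelity, and Section 16 notes that accuracy is sometimes called adherence. The two share the same cut-offs. The reading is plausible, and it makes the correction smaller, but the wording still has to change. A reader might also conclude that chaplains would probably miss Benchmark 1. Without a pooling rule or withdrawal times that cannot be said, and the two cases above fall on opposite sides of the cut-off.

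**Much of the information is collected anyway.** Section 16 reports the modal number and range of sessions, Section 12 has the team ask why a participant withdraws, and the annual report in Section 17 lists reasons for dropout. This limits the harm, but Section 16 does not link any of it to the adherence label.

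**Conclusion.** The point holds, as a minor one, in two parts.

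1. Sections 6 and 7 conflict with Section 10 on sessions (four to eight against eight) and on frequency (2-4 against 4 per week), and Section 16 measures against 8 without calling 4 the minimum. If the bands are used per patient, permitted courses of 4 and 5 sessions are low at 50% and 62.5%. Within the adherence measure they cannot be told apart from early stopping.
2. Adherence Benchmark 1 names chaplains but rests on a measure defined by patients. Followed literally, it counts patient illness and withdrawal against chaplains.

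The consequence is limited. Fidelity is the primary endpoint, the secondary outcome in Section 4 is the number of sessions completed, and no decision rule depends on the bands. The size in patients cannot be given from the protocol.

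**What to change.** - State one dose, target 8 sessions and minimum 4, in Sections 6, 7, 10 and 16, with one weekly frequency range.
- Keep the bands, but label the percentage as sessions received out of the 8-session target.
- Among all enrolled patients, report the proportions with at least 4 sessions and with at least 6, cross-tabulated with whether the patient remained to the end of HSCT. This separates short courses from early stopping.
- Reword adherence Benchmark 1 to the chaplain measure already defined (accuracy above 80% of session components implemented), or delete it as a duplicate of FOI Benchmark 2. Report session completion at patient level only.

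The cost is protocol wording and one extra table. Session counts, retention status and accuracy are already planned, so no new log field is needed, and patients already treated in the enrolment window of November 2021 to July 2022 can be included.

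A new chaplain measure based on sessions for which the patient was available is best avoided. It would need an extra field and a definition of availability, and it would ease Benchmark 1, possibly during enrolment: the chaplain at 25 / 32 = 78.1% above would move to 25 / 25 = 100%.

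### Adherence Benchmark 2 in Section 16 reuses the retention count of 23, and its 75% mark lies in the moderate band while Benchmark 1 expects high adherence

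*Protocol*

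**What the plan says.** All the figures stand in Section 16 of the protocol, under statistical analysis.

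- **Retention Benchmark 1:** "29 (97%) patients enrolled in the study will complete at least one session of chaplain-delivered CSH".
- **Retention Benchmark 2:** 7 patients lost and 23 with complete data, given as 78.8%. The rate comes from the Day 100 completion of a large transplant trial. Sections 16 and 23 call it conservative, because Day 100 falls about 2.5 months after this study's last time point.
- **Definition of adherence:** "Adherence will be evaluated as the percent of sessions completed by patients", with bands of *low* below 70%, *moderate* 70-80% and *high* above 80%.
- **Adherence Benchmark 1:** "We expect that all chaplain residents will achieve high levels of adherence".
- **Adherence Benchmark 2:** 23 patients begin, complete at least one session and "remain in the study until the end of HSCT (see retention benchmarks below), completing at least 75% (6 out of 8) CSH sessions". The cross-reference points below, but the retention benchmarks stand above.

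The same section warns that patients may be too ill for all 8 sessions, and lists dropping out as a separate possibility. Section 4 makes the number of sessions completed the secondary outcome.

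**The concern.** Benchmark 2 sets two conditions: stay to the end of the transplant admission, and complete at least 6 of 8 sessions. Its count is the one obtained from the first condition alone. The second condition has no rate of its own, although the section gives a reason why some retained patients might miss it.

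The mark that counts as success for a patient, 75%, is also one that the protocol's scale calls *moderate*, while Benchmark 1 expects *high*. Patients lost part-way pull the overall percentage down further. At stake is the feasibility statement on the secondary outcome: the verdict on adherence could depend on which benchmark is quoted.

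**Working it through.** **Inputs (Section 16):** 29 starters (97%); 7 lost and 23 complete; 8 intended sessions; a mark of 6 of 8; bands at 70% and 80%. Not stated, and therefore assumed: the sessions *s* completed by each patient who starts but is lost (range 1 to 7), and the denominator (30 enrolled or 29 starters).

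**1. The plan's own figures.** Implied enrolment is 29/0.97 = 29.9, so 30, which agrees with 7 + 23 = 30. Then 0.97 × 30 = 29.1 (stated 29) and 0.788 × 30 = 23.64 (stated 23; 23/30 is 76.7%). The counts reproduce to within rounding. Patients lost after starting: 29 − 23 = 6.

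**2. The adherent count.** Expected adherent patients = enrolled × retention × *a*, where *a* is the fraction of retained patients who reach 6 of 8. With 30 × 0.788 × *a*, *a* = 1 gives 23.6, *a* = 0.9 gives 21.3 and *a* = 0.8 gives 18.9. At the retention rate used, a count of 23 therefore amounts to *a* = 1. The values 0.8 and 0.9 are illustrations only.

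**3. The band of the mark.** 6/8 = 75%, which is inside 70-80%. This step needs no assumption.

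**4. Sessions completed when both second benchmarks are just met.** Pooled adherence = (23 × 6 + 6*s*) / (8 × denominator).

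| *s* | Sessions | Of 240 (30 enrolled) | Of 232 (29 starters) |
|---|---|---|---|
| 1 | 138 + 6 = 144 | 60.0%, low | 62.1%, low |
| 4 | 138 + 24 = 162 | 67.5%, low | 69.8%, low |
| 7 | 138 + 42 = 180 | 75.0%, moderate | 77.6%, moderate |

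The range is 60-78%, and no cell is *high*. Over starters, the pooled figure is a weighted average of the chaplains' figures. If every chaplain were above 80%, it would be too, so in this scenario at least one chaplain misses Benchmark 1.

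**5. What would reach *high*.** The 23 must average more than (0.8 × 8 × denominator − 6*s*)/23 sessions. With 29 starters and *s* = 7 this is (185.6 − 42)/23 = 6.2. With 30 enrolled it is (192 − 24)/23 = 7.3 for *s* = 4, and (192 − 6)/23 = 8.1 for *s* = 1, which is impossible with 8 sessions.

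**6. Dependence on 30 enrolled.** With 50 enrolled, 39 complete (0.788 × 50 = 39.4) and 48 starters, 9 are lost after starting. Sessions are 39 × 6 + 9*s*, or 243 to 297. That is 60.8-74.3% of 400, or 63.3-77.3% of 384. Step 4 therefore does not hinge on the base of 30.

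**The case against.** **A floor is not a forecast.** The 60-78% range needs all 23 to stop at exactly 6 sessions. If they average 7.5 and the lost starters average 4, the result is (172.5 + 24)/240 = 81.9%, which is *high*. This stands. A reader might infer that the benchmarks contradict each other, or that *high* adherence is out of reach; the documents support neither.

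**The shortfall in the count is conditional.** A reader might also infer that the benchmark of 23 will probably be missed. With 30 enrolled, 78.8% retention and *a* between 0.8 and 0.9, the binomial chance of at least 23 is only 0.08 to 0.32. But the protocol calls that retention rate conservative: at 90% retention and *a* = 0.85 (both assumed), the expected count is 22.95 and the chance is 0.59. Other sections give 50, up to 50, or 30-50 patients, and at 50 enrolled the chance exceeds 0.99 for the same *a*. So no general claim of a likely miss is supported. What remains is that the count has no stated adherence fraction and is tied to a base of 30.

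**Benchmark 1 may concern chaplain delivery.** It speaks of what chaplains achieve, and the paragraph mentions fidelity. If delivery was meant, the clash goes away. But Section 16 names delivery of content *accuracy*, expressly to keep it apart from adherence, and gives fidelity its own benchmark. The sessions-completed reading is the natural one, and under the other reading the wording still needs correcting.

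**Nothing hangs on it.** These are expectations without a go/no-go rule, and the modal number and range of sessions will be reported anyway. This limits the severity but does not remove the inconsistency.

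**Conclusion.** The point holds in a limited form. Adherence Benchmark 2 takes over the retention count of 23 and adds a session condition without a rate, so as an expected count it assumes that every retained patient reaches 6 of 8 at 78.8% retention. Its 75% mark is *moderate* on the protocol's own scale, while Benchmark 1 expects *high*. A trial that just meets the two second benchmarks has 60-78% of sessions completed, and would be classed *low* or *moderate*. That range rests on 1 to 7 sessions for each of the 6 lost starters, a denominator of 30 or 29 patients, and 8 intended sessions each. Sections 6 and 7 allow four to eight sessions, so the last input is itself unsettled.

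Severity is minor to moderate: the secondary outcome's interpretation is affected, and the primary fidelity endpoint is not.

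**What to change.** In Section 16:

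1. State adherence Benchmark 2 as the percentage of patients who begin the intervention and complete at least 75% of intended sessions. Give its expected value as a retention rate to the end of the transplant admission times an explicit adherence fraction, both on that denominator. Derive any count from the number actually enrolled, in place of the fixed 23.
2. State the unit and denominator of Benchmark 1: sessions completed out of sessions intended, over all patients who begin, per chaplain. Set its expected band to agree with Benchmark 2 after the planned losses. If chaplain delivery was meant, refer to accuracy instead.
3. Reconcile the intended number of sessions (eight in Sections 10 and 16, four to eight in Sections 6 and 7), since it is the denominator of the measure.

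Two shortcuts should be avoided. Calling 23 an upper bound would be wrong: with 30 enrolled, 78.8% retention and every retained patient adherent, the chance of more than 23 is 0.54. Relaxing Benchmark 1 to *moderate or high* over starters is not enough by itself, because 162/232 = 69.8% at *s* = 4 is still *low*.

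The cost is a few sentences, with no new data, and possibly a less favourable expected adherence.
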